### 1.2.2 Secondary objectives

The secondary objectives of this study are:

- To demonstrate the superiority of once-weekly injection of efpeglenatide 4 and 6 mg with once-weekly injection of dulaglutide 1.5 mg on glycemic control.

- To demonstrate the superiority of once-weekly injection of efpeglenatide 4 and 6 mg with once-weekly injection of dulaglutide 1.5 mg on body weight.
- To evaluate the safety of once-weekly injection of efpeglenatide 4 and 6 mg and once-weekly injection of dulaglutide 1.5 mg.

### 1.3 DETERMINATION OF SAMPLE SIZE

The sample size calculations are performed based on the primary endpoint, change in HbA1c (%) from Baseline to Week 56.

Assuming a common standard deviation of 1.1%, and the true difference between efpeglenatide and dulaglutide is zero, 300 participants per arm will ensure that the upper bound (UB) of the 2-sided 95% CI of the adjusted mean difference would not exceed 0.3% with 91% power.

Hence, there are 3 parallel dosing arms as follows:

- Efpeglenatide 4 mg, N=300
- Efpeglenatide 6 mg, N=300
- Dulaglutide 1.5 mg, N=300

[figure not shown]
### 1.4 STUDY PLAN

This is a multicenter, 56-week, randomized, open-label for the drug (efpeglenatide and dulaglutide) and double-blind for the doses of efpeglenatide, active-controlled, 3-arm, parallel group Phase 3 study consisting of 3 study periods:

- An up to 3-week Screening Period (with a minimum of 11 days)
- A 56-week open-label, active-controlled Treatment Period, for efficacy and safety assessments
- A 6-week post-treatment Follow-up Period to collect safety information after last dose of Investigational Medicinal Product (IMP) after treatment is completed or permanent treatment discontinued

The maximum study duration per participant will be 65 weeks with treatment lasting for 56 weeks. The graphical study design is shown in [Figure 1](#).

Figure 1 - Study Design Overview

Abbreviations: EOS, end of study; EOT, end of treatment; R, Randomization.

Note: The telephone symbol is used to designate visits conducted by telephone interview.

The end of the study is defined as the date of the last visit of the last participant in the study.

### 1.5 MODIFICATIONS TO THE STATISTICAL SECTION OF THE PROTOCOL

The statistical section of the protocol was never changed in an amendment.

## 1.6 STATISTICAL MODIFICATIONS MADE IN STATISTICAL ANALYSIS PLAN

The statistical analysis plan history table below provides the timing, rationale, and key details for major changes to the statistical analysis features in the statistical analysis plan and/or protocol.

**Table 1 - Statistical analysis plan Statistical changes**

| SAP Version Number | Date Approved | Rationale   | Description of Statistical Changes  |
|---------------------------|----------------------|--|--|
| 2                         | 02-Oct-2020          | Additional analyses provided due to Covid-19 pandemic.   | 
2.2.1 Added analyses for COVID-19 related PDs
 
2.4.4.4.2 Added HbA1c sensitivity analysis due to COVID-19 at Week 56. COVID-19 impact on disposition data will be presented. Assessment of missing data due to COVID-19 added
 
2.4.5.1 COVID-19 related AEs have been added
 
Appendix C Added diagram for identifying missing data due to COVID-19
  |
|                           |                      | Clarification on- and post-study periods; Updated definition of actual treatment group for as-treated analysis; clarified AERSM definitions; Added definitions of ADA responses.   | 
2.1.4 Clarified on-study and post-study observation periods
 
2.3.2 Updated definition of actual treatment group
 
2.4.5.1 Updated definitions of AERSM
 
2.1.5.1 Added definitions for Persistent, Transient and indeterminate ADA response
   |
|                           |                      | Since the study was terminated early, the mITT was added and defined; Added additional sensitivity analysis using retrieved-dropout multiple imputation method and back-up multiple imputation method on the primary endpoint; Removed model-based analyses for the change from baseline in mean 24-hour SMPG and time to initiation of rescue medication; Clarified analysis window for efficacy endpoints. | 
2.3.1. Added mITT population
 
2.4.4.1 Added sensitivity analyses using the retrieved-dropout multiple imputation method and the back-up multiple imputation method (in case of insufficient retrieved dropouts).
 
2.4.4.1 descriptively summarized HbA1c at Week 56 by ADA status only
 
2.4.4.4.3 Removed ANCOVA analysis for changes from baseline in mean 24-hour SMPG. Removed Cox proportional hazard model for time to initiation of rescue analysis.
 
2.5.4 Clarified analysis window for efficacy endpoints at Weeks 30 and 56 in case of missing scheduled visits
 |

## 2 STATISTICAL AND ANALYTICAL PROCEDURES

### 2.1 ANALYSIS ENDPOINTS

#### 2.1.1 Demographic and Baseline characteristics

The Baseline value (except for serum creatinine and eGFR) is defined as the last available value prior to the first dose administration of open-label IMP or the last available value on or before the date of randomization if not treated with the open-label IMP. Note: any assessment undertaken on the day of first dose administration of open-label IMP with missing assessment time will be considered as Baseline.

For serum creatinine and eGFR, baseline is defined as the average of all values before the first dose of the open-label IMP for those randomized and exposed or before randomization for those who were randomized but never exposed to open-label IMP.

All Baseline safety parameters (apart from those listed below) are presented along with the on-treatment summary statistics in the safety sections ([Section 2.4.5](#)).

Summary statistics of baseline efficacy parameters by treatment group and overall will be provided in randomized population.

#### *Demographic characteristics*

Demographic variables are gender (Male, Female), race (Asian, Black or African American, White, Multiple, Other, Not reported, Unknown), age in years (quantitative and qualitative variable: <50, ≥50 and <65, ≥65 and <75, ≥75 years), ethnicity (Hispanic or Latino, not Hispanic or Latino, Not reported, Unknown), region (North America, Eastern Europe (including Hungary and Poland)), and randomization strata (Baseline BMI (quantitative and qualitative variable: <30, ≥30 and <40, ≥40 kg/m^2), HbA1c at screening (<8.0, ≥8.0%)).

Participants counted as multiple races will not be counted in other race categories.

#### *Medical history*

Medical history includes medical or surgical history, alcohol and smoking habits.

Medical and surgical history will be coded using the version of Medical Dictionary for Regulatory Activities (MedDRA) currently in effect at the time of database lock.

Alcohol and smoking habit variables include:

- Alcohol status in the last 12 months (Never, Occasional, At least monthly, At least weekly, At least daily)
- Smoking status (Never, Current, Former)
- Cigarettes smoked (per day)

### ***Disease characteristics at Screening or Baseline***

Diabetes history includes:

- Duration of diabetes (years) derived as: (Date of informed consent – Date of diagnosis of diabetes + 1)/365.25;
- Categories of duration of diabetes (<10, ≥10 years);
- Age at diagnosis of diabetes (years) derived as: Year of diagnosis of diabetes – Year of birth;
- Baseline diabetic microvascular complications (Yes, No) (neuropathy, nephropathy, retinopathy) and retinopathy history (Proliferative, Non-proliferative, Macular Edema);
- Use of anti-diabetic medication, duration of Metformin (years), and daily dose of Metformin (mg) at screening;
- Estimated Glomerular Filtration Rate (eGFR) at baseline (ml/min/1.73m^2);
- Estimated glomerular filtration rate (eGFR) categories at baseline (<15 ml/min/1.73m^2 [End stage renal Disease], ≥15 to <30 ml/min/1.73m^2 [Severe decrease in glomerular filtration rate (GFR)], ≥30 to <60 ml/min/1.73m^2 [Moderate decrease in GFR], ≥60 to <90 ml/min/1.73m^2 [Mild decrease in GFR], and ≥90 ml/min/1.73m^2 [Normal]).

### ***Baseline efficacy variables***

The baseline efficacy variables include:

- HbA1c (% , mmol/mol);
- HbA1c category (<8.0, ≥8.0%)
- FPG (mmol/L, mg/dL);
- Body weight (kg);
- Waist Circumference (cm)
- Mean 24-hour SMPG (mmol/L, mg/dL)

Any technical details related to computation, dates, and imputation for missing dates are described in [Section 2.5](#).

### 2.1.2 Prior or concomitant medications

Any medication or vaccine (including over-the-counter or prescription medicines, vitamins, and/or herbal supplements) that the participant is receiving at the time of enrollment or during the study must be recorded in the corresponding case report form page.

All medications will be coded using the World Health Organization-Drug Dictionary (WHO-DD) using the version currently in effect at the time of database lock.

Medications will be classified into the following 3 groups:

- Prior medications are those the participant used prior to first open-label IMP administration. Prior medications can be discontinued before first open-label IMP administration or can be ongoing during treatment phase.
- Concomitant medications are any treatments received by the participant concomitantly to the IMP(s), from first dose to the end of treatment + 30 days (+ 7 days for antidiabetic drugs). A given medication can be classified both as a prior medication and as a concomitant medication. Concomitant medications do not include medications started during the posttreatment period (as defined in the observation period in [Section 2.1.4](#)).
- Post-treatment medications are those the participant took in the period running from the 31st day (8 days for antidiabetic drugs) after the last injection of IMP up to the end of the study.

### Background medication

Metformin tablets, administered as per Principal Investigator prescription and in accordance with local labeling, and rescue medication(s) that will be used to treat hyperglycemia if a participant's glycemic values reach the applicable rescue threshold.

The doses of metformin at randomization should be maintained throughout the study unless down-titration is required for safety reasons.

**Rescue medication(s)** is considered Non-IMP (NIMP) treatment. Except for GLP-1 RA and DDP-4i, any approved medication(s) including oral antidiabetic drugs or insulin can be prescribed at the Investigator's discretion to treat the hyperglycemia.

The background medication and rescue medications will be included in the concomitant medication summaries. A special list of rescue therapy medications will be generated.

### Prohibited medication(s)

All prohibited medications are based on sponsor-defined Customized Drug Grouping (CDG).

The following treatments are prohibited during the Screening Period and the 56 weeks of treatment period.

- Initiation of any antidiabetic agents other than the IMP or change in dose or preexisting oral anti-diabetic(s) (OAD) before pre-rescue assessments and initiation of rescue therapy (short-term use [ $<10$  consecutive days] of short-acting insulin for treatment of acute illness or surgery is allowed)
- Initiation of any GLP-1 RAs (eg, exenatide, liraglutide, or semaglutide) and DPP-4 inhibitors (eg, sitagliptin, saxagliptin, vildagliptin, or linagliptin)
- Initiation of any prescription weight loss drugs (eg, phentermine, lorcaserin, or orlistat)
- Gastric surgery or other gastric procedures for weight loss
- Systemic use of glucocorticoids for more than 10 consecutive days (topical, nasal spray, and inhaled or intra-articular applications are allowed)
- Any investigational drug other than IMP for this study

Any technical details related to computation, dates, imputation for missing dates are described in [Section 2.5](#).

### **2.1.3 Efficacy endpoints**

Efficacy endpoints are defined in [Section 2.1.3.1](#), [Section 2.1.3.2](#) and [Section 2.1.3.3](#).

Efficacy variables will be summarized in both standard international units and conventional units when applicable.

#### **2.1.3.1 Primary efficacy endpoint**

- Change in HbA1c (%) from Baseline to Week 56

#### **2.1.3.2 Secondary efficacy endpoints**

- Number of participants with HbA1c  $< 7.0\%$  at Week 56 (yes/no)
- Change in FPG from Baseline to Week 56
- Changes in body weight from Baseline to Week 56

#### **2.1.3.3 Exploratory efficacy endpoint(s)**

- Participant perspective on benefit/risk of the drug using the Patient qualitative assessment of treatment version 2 (PQAT v2) at Weeks 30 and 56
- Number of participants with HbA1c  $< 7.0\%$  at Week 30 (yes/no)

- Change in HbA1c from Baseline to Week 30
- Change in FPG from Baseline to Week 30
- Changes in 7-point SMPG profiles (mmol/L, mg/dL: mean 24-hour SMPG) from Baseline to Weeks 30 and 56
- Change in plasma glucose excursions (2-hours PPG minus preprandial plasma glucose at breakfast, lunch, and dinner) based on 7-point SMPG data from baseline to Week 30 and Week 56
- Number of participants with rescue therapy used during the treatment period until Weeks 30 and 56 (yes/no)
- Time to initiation of rescue therapy (weeks)
- Change from baseline to week 30 in body weight
- Number of participants with change in body weight  $\geq 5\%$  from Baseline to Week 56 (yes/no)
- Number of participants with change in body weight  $\geq 10\%$  from Baseline to Week 56 (yes/no)
- Change in waist circumference from Baseline to Weeks 30 and 56

Mean 24-hour SMPG is the average over the available plasma glucose values from the 7 time points and can only be calculated if at least 4 points are available.

Prandial glucose excursions are calculated by subtracting the preprandial value from the postprandial value respectively for breakfast, lunch, and dinner.

#### 2.1.4 Safety endpoints

The safety analysis will be based on the reported adverse events (AE), hypoglycemia and other safety information, such as clinical laboratory data, vital signs, and ECG.

##### *Observation period*

The period related to treatment will be divided into 3 main segments:

- The **pre-treatment** period is defined as the time from informed consent up to the time of first injection of open-label IMP
- The **on-treatment** period is defined as the time from the first injection of the open-label IMP up to 30 days (7 days for hypoglycemia) after the last injection of the IMP
- The **post-treatment** period is defined as the period from the end of the on-treatment period.

The **on-study observation period** is defined as the time from first injection of open-label IMP up to either the last protocol-planned visit or the date of last available information if participants discontinue the study prematurely, whichever is later.

The **post-study observation period** is defined as the time after the end of the on-study observation period until the date of resolution/stabilization of SAE, AESI, and AERSM, up to database lock.

#### **2.1.4.1 Adverse events variables**

##### ***Adverse event observation period***

- **Pre-treatment AEs** are AEs that developed or worsened or became serious during the pre-treatment period
- **Treatment-emergent AEs (TEAEs)** are AEs that developed or worsened or became serious during the on-treatment period
- **Post-treatment AEs** are AEs that developed or worsened or became serious during the post-treatment period

All AEs (including SAEs, AEs of special interest and AEs requiring specific monitoring) will be coded to a lower-level term (LLT), preferred term (PT), high-level term (HLT), high-level group term (HLGT), and associated primary system organ class (SOC) using the version of MedDRA currently in effect at the time of database lock.

Adverse events of special interest (AESIs) include the following:

- Pregnancy of a female participant entered in a study as well as pregnancy occurring in a female partner of a male participant entered in a study with IMP/NIMP.
- Symptomatic overdose (serious or nonserious) with IMP/NIMP
- Increase in alanine aminotransferase (ALT) >3 x upper limit normal (ULN)

Adverse events requiring specific monitoring include the following terms:

- Severe gastrointestinal (GI) events
- Severe hypoglycemia
- Pancreatic events (including abnormal values of pancreatic enzymes, pancreatitis and pancreatic neoplasm)
- Selected cardiovascular events (CV death, MI, stroke, heart failure leading to hospitalization, unstable angina, and transient ischemic attack (TIA))
- Calcitonin increase ( $\geq 5.9$  pmol/L ( $\geq 20$  pg/mL)) and thyroid C-cell neoplasm
- Acute renal failure
- Diabetic retinopathy complications

- Severe injection site reaction
- Severe allergic reactions
- Severe immune complex disease

Independent Clinical Endpoint Committee(s) [CEC(s)] will review, assess and/or adjudicate all events of death, selected CV events and pancreatic events.

#### **2.1.4.2 Deaths**

The death observation periods are per the observation periods defined below.

- Death on-study: deaths occurring during the on-study observation period
- Death on-treatment: deaths occurring during the on-treatment period
- Death post-study: deaths occurring after the end of the study

#### **2.1.4.3 Laboratory safety variables**

Clinical laboratory data consists of blood analysis, including hematology, clinical chemistry and urinalysis. Clinical laboratory values will be summarized in both standard international units and conventional units (US) when applicable.

Blood samples for clinical laboratories will be collected at designated visits (see Schedule of Activities in [Appendix D](#)). The following laboratory parameters will be measured at central laboratory:

- Hematology
  - Red blood cells and platelets: Platelet count, Red blood cell count, Hemoglobin, Hematocrit;
  - White blood cells: White blood cell count, differential count (Neutrophils, Lymphocytes, Monocytes, Eosinophils, Basophils).
- Clinical chemistry
  - Pancreatic enzymes: Amylase, Lipase;
  - Electrolytes: Potassium, Sodium;
  - Renal function: Creatinine, Estimated glomerular filtration rate (MDRD formula);
  - Liver function: Alanine aminotransferase (ALT), Aspartate aminotransferase (AST), Alkaline phosphatase (ALP), Total bilirubin.
  - Lipid profile: Triglyceride, Total cholesterol, Low-density lipoprotein cholesterol, High-density lipoprotein cholesterol

For triglycerides, only values assessed in fasted patients will be analyzed.

  - Calcitonin

Technical formulas are described in [Section 2.5.1](#).

#### **2.1.4.4 Vital signs variables**

Vital signs include sitting heart rate (bpm), as well as sitting systolic and diastolic blood pressures (mmHg).

#### **2.1.4.5 Electrocardiogram variables**

ECG variables will include 12-lead ECG interpretation (normal/abnormal) provided by the investigator. 12-lead ECG recording will be performed locally at Randomization, Week 12 and Week 56. Investigator's interpretation of normal and abnormal will be reported in the eCRF.

#### **2.1.4.6 Hypoglycemia**

During the study, participants are to be instructed to document any hypoglycemic episodes in their study diary. Hypoglycemia will be reported in the specific eCRF page with onset date and time, symptoms and/or signs, the SMPG value if available, and the treatment of the hypoglycemia. Hypoglycemia fulfilling the seriousness criteria will be documented, in addition, on the SAE form in the eCRF.

Hypoglycemic events will be categorized as follows:

- **Severe hypoglycemia:** Severe hypoglycemia is an event requiring assistance of another person to actively administer carbohydrate, glucagon, or other resuscitative actions. These episodes may be associated with sufficient neuroglycopenia to induce seizure, unconsciousness or coma. Plasma glucose measurements may not be available during such an event, but neurological recovery attributable to the restoration of plasma glucose to normal is considered sufficient evidence that the event was induced by a low plasma glucose concentration. The definition of severe symptomatic hypoglycemia includes all episodes in which neurological impairment was severe enough to prevent self-treatment and which were thus thought to place participants at risk for injury to themselves or others. Note that "requiring assistance of another person" means that the participant could not help himself or herself. Assisting a participant out of kindness, when assistance is not required, should not be considered a "requiring assistance" incident.

Severe hypoglycemia will be qualified as an SAE only if it fulfills SAE criteria. For example, events of seizure, unconsciousness or coma must be reported as SAEs.

- **Documented symptomatic hypoglycemia:** Documented symptomatic hypoglycemia is an event during which typical symptoms of hypoglycemia are accompanied by a measured plasma glucose concentration less than or equal to 3.9 mmol/L ( $\leq 70$  mg/dL). Clinical symptoms that are considered to result from a hypoglycemic episode are, eg, increased sweating, nervousness, asthenia/weakness, tremor, dizziness, increased appetite, palpitations, headache, sleep disorder, confusion, seizures, unconsciousness, or coma.

- **Asymptomatic hypoglycemia:** Asymptomatic hypoglycemia is an event not accompanied by typical symptoms of hypoglycemia but with a measured plasma glucose concentration less than or equal to 3.9 mmol/L ( $\leq 70$  mg/dL).
- **Probable symptomatic hypoglycemia:** Probable symptomatic hypoglycemia is an event during which symptoms of hypoglycemia are not accompanied by a plasma glucose determination, but was presumably caused by a plasma glucose concentration less than or equal to 3.9 mmol/L ( $\leq 70$  mg/dL); symptoms treated with oral carbohydrate.
- **Relative hypoglycemia:** (recently termed “pseudo-hypoglycemia”) is an event during which the person with diabetes reports any of the typical symptoms of hypoglycemia, and interprets the symptoms as indicative of hypoglycemia, but with a measured plasma glucose concentration greater than 3.9 mmol/L ( $> 70$  mg/dL).

In addition to the threshold of plasma glucose of less than or equal to 3.9 mmol/L ( $\leq 70$  mg/dL), documented symptomatic and asymptomatic hypoglycemic events with measured plasma glucose concentration  $\geq 3.0$  and  $< 3.9$  mmol/L ( $\geq 54$  and  $< 70$  mg/dL), and less than 3.0 mmol/L ( $< 54$  mg/dL) will also be analyzed.

Hypoglycemic events will be evaluated regardless of the time of onset during the study and time of the day.

In addition, hypoglycemia events will be evaluated at the following time periods defined by time of the day:

- **Nocturnal hypoglycemia defined by time of the day:** any hypoglycemia of the above categories that occurs between 00:00 and 05:59, regardless of whether participant was awake or woke up because of the event.
- **Daytime hypoglycemia:** any hypoglycemia of the above categories that occurs between 06:00 and 23:59.

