- **Asymptomatic hypoglycemia:** Asymptomatic hypoglycemia is an event not accompanied by typical symptoms of hypoglycemia but with a measured plasma glucose concentration  $\leq 3.9$  mmol/L ( $\leq 70$  mg/dL).
- **Probable symptomatic hypoglycemia:** Probable symptomatic hypoglycemia is an event during which symptoms of hypoglycemia are not accompanied by a plasma glucose determination, but was presumably caused by a plasma glucose concentration  $\leq 3.9$  mmol/L ( $\leq 70$  mg/dL); symptoms are treated with oral carbohydrate.
- **Relative hypoglycemia:** (recently termed “pseudo-hypoglycemia”) is an event during which the person with diabetes reports any of the typical symptoms of hypoglycemia, and interprets the symptoms as indicative of hypoglycemia, but with a measured plasma glucose concentration greater than 3.9 mmol/L (70 mg/dL).

In addition to the threshold of plasma glucose of  $\leq 3.9$  mmol/L (70 mg/dL), documented hypoglycemia with a measured plasma glucose concentration between 3.0 to 3.9 mmol/L (54 to 70 mg/dL) and less than 3.0 mmol/L ( $< 54$  mg/dL) will also be analyzed (6).

Hypoglycemic events will be evaluated regardless of the time of onset during the study and time of the day.

In addition, hypoglycemia events will be evaluated at the following time periods defined by time of the day:

- **Nocturnal hypoglycemia defined by time of the day:** any hypoglycemia of the above categories that occurs between 00:00 and 05:59, regardless of whether participant was awake or woke up because of the event
- **Daytime hypoglycemia:** any hypoglycemia of the above categories that occurs between 06:00 and 23:59

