### **2.4.5.2 Analysis of Hypoglycemia**

Treatment-emergent hypoglycemia events will be tabulated separately from the AEs.

Event frequency and incidence of hypoglycemia events will be summarized by treatment for all reported hypoglycemia and per type of hypoglycemic event described in [Section 2.1.4.6](#) (ie, severe, documented symptomatic, asymptomatic, probable symptomatic, relative) for safety population. Incidence of severe or documented symptomatic hypoglycemia events will be summarized by study period ( $\leq 4$  weeks (titration period),  $> 4$  weeks to  $\leq 8$  weeks,  $> 8$  weeks to  $\leq 30$  weeks,  $> 30$  weeks) and according to time of occurrence (nocturnal [ie, 00:00 to 05:59 am], daytime [ie, 06:00 am to 23:59]) for safety population. Documented hypoglycemia (symptomatic or asymptomatic) will be also evaluated for the more stringent plasma glucose threshold of  $< 54$  mg/dL (3.0 mmol/L), as well as for  $\geq 3.0$  and  $< 3.9$  mmol/L ( $\geq 54$  and  $< 70$  mg/dL). Frequency and percentage of participants with at least one hypoglycemia event will be summarized as well.

Event rate of hypoglycemia per participant year will be calculated by treatment using the total number of hypoglycemia events from all participants (denoted as n) divided by the total exposures from all participants expressed in years (ie, participant exposure in days divided by 365.25, denoted as t). Multiple events from an individual participant will all be counted. Event rates of hypoglycemia per participant year {all reported hypoglycemia, severe, documented symptomatic [ $< 54$  mg/dL ( $< 3.0$  mmol/L),  $\geq 54$  and  $< 70$  mg/dL ( $\geq 3.0$  and  $< 3.9$  mmol/L),  $\leq 70$  mg/dL ( $\leq 3.9$  mmol/L) respectively], asymptomatic, probable symptomatic, relative hypoglycemia} will be presented by treatment group during the 56-week on-treatment period.

The summary of frequency and event rate in participant years for severe or documented symptomatic hypoglycemia will be provided as appropriate by gender (Male, Female), age group ( $< 50$ ,  $\geq 50$  to  $< 65$ ,  $\geq 65$  to  $< 75$ ,  $\geq 75$  years), and race (Asian, Black or African American, White, Other).

A KM curve will also be provided by treatment group for the time to first severe or documented symptomatic hypoglycemia during the on-treatment period.

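### The SAP's intermediate hypoglycemia band stops short of 3.9 mmol/L (70 mg/dL), so events at exactly that limit are counted in the total but in neither glucose band

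*SAP*

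**What the plan says.** **Event definitions, SAP 2.1.4.6.** The upper limit is inclusive for both documented types. In a documented symptomatic event, "typical symptoms of hypoglycemia are accompanied by a measured plasma glucose concentration less than or equal to 3.9 mmol/L" (70 mg/dL). An asymptomatic event is "not accompanied by typical symptoms of hypoglycemia but with a measured plasma glucose concentration less than or equal to 3.9 mmol/L". Relative hypoglycemia has symptoms "but with a measured plasma glucose concentration greater than 3.9 mmol/L".

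**Bands, SAP 2.1.4.6.** The additional cuts open with "In addition to the threshold of plasma glucose of less than or equal to 3.9 mmol/L" and apply to "documented symptomatic and asymptomatic hypoglycemic events with measured plasma glucose concentration" in two ranges: at least 3.0 and below 3.9 mmol/L (at least 54 and below 70 mg/dL), and below 3.0 mmol/L (54 mg/dL).

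**Analysis, SAP 2.4.5.2.** "Documented hypoglycemia (symptomatic or asymptomatic) will be also evaluated for the more stringent plasma glucose threshold of" 54 mg/dL (3.0 mmol/L), and also for the intermediate band with the same strict upper limit. For event rates of documented symptomatic hypoglycemia, the section lists three cuts together: below 54, at least 54 and below 70, and at or below 70 mg/dL.

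**Protocol 8.2.5.** The additional analysis covers "documented hypoglycemia with a measured plasma glucose concentration between 3.0 to 3.9 mmol/L (54 to 70 mg/dL"), together with readings below 3.0 mmol/L.

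**Data capture, Protocol 1.3 (repeated in SAP Appendix D).** The hypoglycemia eCRF page is required for every self-monitored value at or below 3.9 mmol/L (70 mg/dL), so readings at the limit are meant to be in the database.

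**The concern.** The event definition closes at 3.9 mmol/L and the band opens just below it. A documented event at the limit is an event and is not relative hypoglycemia, yet it has no band. The strict sign appears in both units in three statements across two sections, so it would be programmed as written.

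At stake is the internal consistency of one safety table. A reader who sees two adjoining bands beside what looks like their total will expect event counts and rates to reconcile. Programmers would have to publish rows that do not reconcile or depart from the SAP without saying so.

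**Working it through.** The plan states no figure for this point, so there is none to reproduce. The check assigns every displayable reading to the SAP's cuts and compares the bands with the total.

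**Inputs (SAP 2.1.4.6 and 2.4.5.2)**

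| Cut | mmol/L | mg/dL |
|---|---|---|
| Total (documented event) | ≤3.9 | ≤70 |
| Lower band | <3.0 | <54 |
| Intermediate band | ≥3.0 and <3.9 | ≥54 and <70 |

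Assumed display steps are 0.1 mmol/L and 1 mg/dL. The grids start at 1.0 mmol/L and 20 mg/dL; the starting points do not affect which value is left over.

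**As written**

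- mmol/L, 1.0 to 3.9: 20 values in the lower band + 9 in the intermediate band = 29, against 30 in the total. Left over: 3.9.
- mg/dL, 20 to 70: 34 + 16 = 50, against 51. Left over: 70.

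**With the upper limit closed (≤3.9, ≤70)**

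- mmol/L: 20 + 10 = 30 of 30.
- mg/dL: 34 + 17 = 51 of 51.

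**Share of possible values.** In the closed band the boundary is 1/10 = 10% of the mmol/L values and 1/17 = 5.9% of the mg/dL values. These are shares of displayable values. They would be shares of events only if readings were spread evenly over the band, which the documents do not say.

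**What is additive.** SAP 2.4.5.2 computes a rate as events n over exposure t. With the same t in each row, rates add when event counts add. Numbers of participants with at least one event need not add even with closed bands, because one participant can have events in both.

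**Units, a separate matter.** The SAP's own pair implies 54/3.0 = 18 mg/dL per mmol/L. Then 70/18 = 3.889 mmol/L and 3.9 × 18 = 70.2 mg/dL. With a more exact factor of 18.016 (an assumption, not in the documents), 70/18.016 = 3.885, 3.9 × 18.016 = 70.26 and 54/18.016 = 2.997. A reading of 70 mg/dL is therefore outside the SAP band by the mg/dL limit and inside it by an unrounded mmol/L limit. With the more exact factor, 54 mg/dL is in the intermediate band by one unit and in the lower band by the other.

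**The case against.** The strongest reply is that almost nothing depends on this row. The secondary safety endpoints in Protocol section 3 are participants with at least one hypoglycemic event and events per participant-year, and neither is defined by a band. An event at the limit stays in all reported hypoglycemia, in its own type and in the ≤3.9 mmol/L rate. SAP 2.4.5 calls the safety analysis essentially descriptive, with no systematic testing. For documented symptomatic event rates, the missing part can be recovered by subtracting both bands from the total. All of this stands. A reader might infer that hypoglycemia endpoints are under-reported; the documents do not support that.

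Second, neither document says that the bands must sum to the total. That is correct, and additivity is an inference. It is a fair one, because the SAP lists the two bands beside the total and nothing in it explains leaving out a single value.

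Third, the protocol is weaker authority than it looks. Its range does not say whether the ends are included, its Table 6 names only the threshold below 3.0 mmol/L, and its amendment summary says that the range was added to match the SAP. This also stands. The case for closing the limit rests first on the SAP's own event definition, with the natural reading of Protocol 8.2.5 as support.

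Fourth, the unit mismatch might be read as a result of the strict sign. It is not. It comes from pairing rounded limits, it also touches the event definition and the 3.0 mmol/L cut, and closing the upper limit does not remove it.

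**Conclusion.** The gap holds as a matter of text: at exactly 3.9 mmol/L or 70 mg/dL, a documented event belongs to the total and to neither band. The consequence is confined to the intermediate-band counts and rates, which can only be too low relative to a band closed at the event limit, and to their failure to reconcile with the total. The primary analysis is untouched.

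The number of events affected cannot be computed. The documents support only the statement that the boundary is one of 10 or one of 17 displayable values, depending on the unit. A percentage of events lost might be inferred from that, but it would depend entirely on the assumed shape of the readings. The conclusion assumes meters that display 0.1 mmol/L or 1 mg/dL steps, and that the bands are meant to subdivide the documented events. This is a minor correction worth making before the tables are programmed.

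**What to change.** In SAP 2.1.4.6, and in both places in 2.4.5.2, write the upper limit of the intermediate band as ≤3.9 mmol/L (≤70 mg/dL). That is three statements in two units, so six inequality signs, plus any matching labels in the table shells.

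As a separate sentence, state that each reading is classified in the unit in which it was recorded, against the limit given in that unit and without conversion. This settles the rounding question at both cuts.

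Neither change needs new data or affects any test.
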